6.3 MEASURES TO MINIMIZE BIAS: RANDOMIZATION AND BLINDING

As previously described, participants will be block-randomized with a 1:1:1 allocation ratio (placebo: caffeine 1.5 mg/kg: caffeine 3 mg/kg). Randomization will also be stratified by age (<75 or ≥75 years old) and sex. Older age is a risk factor for delirium, with patients 75 years of age and older having particularly high risk.¹³⁻¹⁵ Response to caffeine may also differ based on sex.⁸⁸ Stratified randomization will thus help to balance these biologically relevant, prognostic variables and mitigate selection bias. Additionally, research teams, patients, clinicians, and analysts will remain blinded to the study drug intervention. Regression models will also include adjustments for relevant confounders, and baseline imbalances, as described in **Section 9, Statistical Considerations**. Blinding can be broken, if necessary, per the physicians caring for the subject to ensure subject safety.

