8.2 SAFETY AND OTHER ASSESSMENTS

The following additional procedures will be conducted to assess for respective safety outcomes and events:

- **Vital signs** (e.g., temperature, pulse, respirations, blood pressure). Vitals will be collected clinically per perioperative standards and protocols. These data will be collected and analyzed in relation to study drug administration, with particular focus on cardiovascular Adverse Events (AEs) (**See Section 9.4.4., Safety Analyses**).
- **Assessment of adverse events.** Assessment for Adverse Events (AEs) will occur throughout the study period (**Section 1.3, Schedule of Activities, SoA**) as described in following sections.
- **Baseline caffeine intake.** Habitual caffeine intake will be assessed among participants and categorized into no daily intake or any daily intake.
- **Baseline cognitive function.** Baseline cognitive function will be assessed via AD8 Dementia Screening Interview, Montreal Cognitive Assessment, and Cognitive Instrumental Activities of Daily Living.
- **Instrumental Activities of Daily Living.** Instrumental Activities of Daily Living will be assessed to determine preoperative functional status.
- **Postoperative nausea and vomiting.** Measured via the Postoperative Nausea and Vomiting Intensity Scale⁸⁹ in the PACU, postoperative day one afternoon, and postoperative day two afternoon. Any vomiting and antiemetic use from PACU admission through postoperative day two hours will also be recorded.
- **Arrhythmias.** Any new cardiac arrhythmia not previously experienced by the patient will be reported from PACU admission through postoperative day two.
- **Restraint use.** Any instance of restraint use related to altered mental status will be recorded.
- **Injury to self or others.** Any injury to self or others resulting from agitation/altered mental status
- **Falls.** Fall presence as reported by the patient, hospital staff, or medical record.

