9.4.2 ANALYSIS OF THE PRIMARY EFFICACY ENDPOINT(S)

As previously described, postoperative delirium will serve as the primary endpoint. The primary analytical test will be a multivariable logistic regression model that will follow the GEE approach. Independent variables will include the placebo group (reference), low-dose caffeine group, high-dose caffeine group, and *a priori* variables that may be independently predictive of delirium (e.g., age, male sex, American Society of Anesthesiologists Physical Status score, baseline cognitive function via Montreal Cognitive Assessment, baseline functional status via Instrumental Activities of Daily Living, depression, and epidural use⁸³). Baseline cohort imbalances, defined by absolute standardized differences >0.20, will also be included in this model.

Lastly, missing delirium data will be assessed for randomness using the Little's Missing Completely at Random Test. If data are missing at random, imputation will be performed, and these results will be compared to results with the actual data in the supplementary appendix. If data are not missing at random, no imputation will be performed, and the Cochran-Armitage test will be used to assess for the proportion of missing data across each arm.

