9.4.3 ANALYSIS OF THE SECONDARY ENDPOINT(S)

For secondary endpoints, a similar GEE-based approach will be used. Within- and between- group comparisons will be analyzed based on coefficients in the model. This approach also allows for flexibility with missing data. Unstandardized beta coefficients will be presented with 95% confidence intervals and p-values (<0.05 will be considered statistically significant).

For non-repeated continuous measures (e.g., delirium duration, cumulative opioid consumption) and binary outcomes (e.g., postoperative delirium, headache), we will use the same GEE modeling approach. All GEE models will use the empirical parameter estimates with an exchangeable correlation matrix. As indicated previously, models will adjust for baseline cohort imbalances. Additionally, for Quality of Recovery and headache severity, the differential effect of habitual caffeine consumption and group will be tested. This will be tested via interaction term of habitual caffeine consumption with caffeine group (placebo, low-dose caffeine group, high-dose). The daily number of caffeinated beverages will be recorded for each participant, and the resulting distribution will be analyzed and used to inform the most appropriate categorization of habitual caffeine users (e.g., non-users, low-dose, high-dose, etc.).

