9.4.5 BASELINE DESCRIPTIVE STATISTICS

Study arms will be compared on baseline characteristics, including demographics and medical comorbidities. Absolute standardized differences will be used to compare groups at baseline.

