10.1.6 SAFETY OVERSIGHT

In conjunction with the National Institute on Aging, an independent Data and Safety Monitoring Board (DSMB) will be commissioned. The DSMB will be composed of individuals with the appropriate expertise who will guide the National Institute on Aging representatives and the study investigators. The DSMB will be comprised of external members with no direct involvement in the trial.

The DSMB members will have appropriate – and complementary – context expertise (e.g., anesthesiologists, biostatisticians with clinical trials experience, etc.). DSMB members will not have conflicts of interest – financial, proprietary, professional, or otherwise – that could threaten impartial, independent decision-making responsibilities. The DSMB charter will be drafted and approved by all relevant parties, and meetings will occur twice per year. The trial statistician team will be responsible for compiling and curating data into reports for the DSMB.

The DSMB meetings will focus mainly on the following study elements: safety data (e.g., postoperative nausea and vomiting, arrhythmias, falls, etc.), data quality, and enrollment data and projections. The DSMB may consider early study termination based on safety concerns, but there are no plans to terminate the study early based on apparent benefit or futility. Adequate statistical power, with the pre-specified sample size, will be required for the primary analysis along with pre-specified subgroup analyses (e.g., patients with Mild Cognitive Impairment). Early trial termination may result in effect size inflation compared to those not stopped early.⁹⁴⁻⁹⁶ The effect of caffeine on secondary outcomes (e.g., delirium severity, quality of recovery, etc.) is also important, and early termination would attenuate these analyses. As such, there will be no plan for early trial termination based on perceived efficacy or futility with respect to the primary outcome of delirium.

Lastly, the DSMB will hold both open and closed sessions. Open sessions will focus on overall status of the trial, pooled data analysis, and overarching concerns (e.g., enrollment, data quality). The objective of the closed sessions will be to review safety data, effectiveness outcomes, and adverse events, in an unblinded manner.

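### The primary model adds covariates according to observed baseline imbalance (>0.20), so the covariate set is fixed by chance; the cost is a data-dependent odds ratio and a modest loss of precision

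*Protocol*

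**What the plan says.** Section 9.4.2 makes a multivariable logistic regression, fitted by GEE with placebo as reference, the primary test. It adjusts for "variables that may be independently predictive of delirium (e.g., age, male sex, American Society of Anesthesiologists Physical Status score" and goes on to baseline cognition (MoCA), functional status (IADL), depression and epidural use: seven variables, offered as examples. It then adds a rule: "Baseline cohort imbalances, defined by absolute standardized differences >0.20, will also be included in this model". Section 9.4.3 says the secondary models adjust for baseline imbalances as well, and section 6.3 announces the same.

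The variables screened come from section 9.4.5: "Study arms will be compared on baseline characteristics, including demographics and medical comorbidities". The metric comes from the same place: "Absolute standardized differences will be used to compare groups at baseline". A standardised difference compares two groups and this trial has three. The protocol does not say whether the rule looks at any pair, at each caffeine arm against placebo, or at an average.

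**The concern.** Under randomisation, a difference between arms in a baseline variable is a chance event. Its size does not show whether the variable predicts delirium, and prognostic strength is the reason to adjust. A rule keyed to imbalance therefore selects on the wrong property. The variables the investigators believe to be prognostic are already named.

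Two things are at stake. First, an adjusted odds ratio is conditional on the covariates in the model, so the quantity reported as the primary result depends on which variables were tabulated and which happened to cross 0.20. Second, each added term uses information from a limited number of delirious patients, which widens the interval and, in a logistic model, tends to move the estimate away from zero.

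**Working it through.** **Inputs from the protocol.** N = 250 with 1:1:1 allocation, so about 83 per arm (sections 9.2, 4.1). Imbalance is judged on everyone randomised, since the primary analysis is intention-to-treat (9.3). Trigger 0.20 (9.4.2). Delirium 30% on placebo, 10–30% on low dose, 10–15% on high dose (9.2). Two-sided alpha 0.05 (9.2, 9.4.1).

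**The plan's own figure.** The protocol gives no trigger rate to reproduce. Its only related figure is 80–95% power. With a 2-df chi-square test and one outcome per patient, rates of 30/10/10% give 95.7%, which matches the upper end. Rates of 30/30/15% give 63%, so the lower end does not reproduce on that basis. A repeated-measures calculation (7 assessments, correlation about 0.6–0.65) reaches about 80%, but the protocol states no correlation. Nothing below depends on this figure.

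**Step 1: chance of crossing 0.20 for a balanced covariate, n = 83 per arm.**
- One given pair: SE = √(2/83) = 0.155; 0.20/0.155 = 1.29; 2 × (1 − Φ(1.29)) = 19.8%.
- Any of three pairs: P(range of three standardised means > 0.20 × √83 = 1.82), from the studentised range, = 40.2%. Simulation with 200,000 replicates gave 40.4% for continuous and 38–41% for binary covariates.
- Either caffeine arm against placebo: about 33%.
- Average of the three pairwise values: for three groups this is two-thirds of the range, so the range must exceed 0.30; 0.30 × √83 = 2.73; probability 13.0%.

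At 75 per arm (after 10% dropout) the last three become 43.8%, about 37% and 15.8%.

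**Step 2: how many terms enter.** The number of unlisted candidates is not in the protocol. Assuming 10 to 20, independent of each other:

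| Reading | Chance per variable | Expected extra terms |
|---|---|---|
| Average of pairs | 13% | 1.3–2.6 |
| Either caffeine arm vs placebo | 33% | 3.3–6.6 |
| Any pair | 40% | 4–8 |

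Under the any-pair reading, the chance of at least one addition among 10 candidates is 1 − 0.598^10 = 99.4%.

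**Step 3: events per parameter.** At 30/10/15%, 83.3 × (0.30 + 0.10 + 0.15) ≈ 46 delirious patients, counting one outcome per patient. Fixed model: 2 arm terms + 7 covariates = 9 parameters, 46/9 = 5.1 each. With 4 extras, 46/13 = 3.5; with 8 extras, 46/17 = 2.7.

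**Step 4: effect on the estimate.** Ordinary logistic models were simulated with 7 fixed covariates, with and without the triggered extras under the any-pair reading, 1,000 replicates per scenario. The coefficient is the high-dose log odds ratio. Candidates were either non-prognostic or weakly prognostic (coefficient 0.2).

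| Candidates | Treatment effect | SD fixed → rule | Mean fixed → rule | Rejection fixed → rule |
|---|---|---|---|---|
| 10, non-prognostic | present | 0.469 → 0.480 (+2%) | −1.047 → −1.076 | 66.3% → 66.0% |
| 10, weak | none | 0.378 → 0.392 (+4%) | about 0 | 5.4% → 5.2% |
| 10, weak | present | 0.429 → 0.457 (+7%) | −0.998 → −1.048 | 65.8% → 66.1% |
| 20, non-prognostic | none | 0.386 → 0.417 (+8%) | about 0 | 4.7% → 5.2% |
| 20, non-prognostic | present | 0.471 → 0.523 (+11%) | −1.061 → −1.110 | 69.1% → 66.9% |
| 20, weak | none | 0.373 → 0.411 (+10%) | about 0 | 4.7% → 4.7% |
| 20, weak | present | 0.438 → 0.494 (+13%) | −0.947 → −1.053 | 62.5% → 63.2% |

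In the eighth scenario (10 non-prognostic candidates, no treatment effect) the SD went from 0.382 to 0.396 (+4%). The SD therefore rises 4–13% in seven of eight scenarios and 2% in the other. The mean moves 0.03–0.11 away from zero where an effect exists.

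**The case against.** The strongest defence is that the rule is itself pre-specified. It has a stated threshold, never looks at outcomes, and can be applied mechanically under masked arm labels. The simulation supports this: type I error stays near 5% and power barely moves. That stands, and a reader should not infer that the primary analysis is invalid or left to free choice. What the rule leaves open is the covariate set, and with it the conditional odds ratio.

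A second objection is that 40% is only one reading. That is right: the range is 13–40% at 83 per arm. The candidate count is also an assumption, comorbidities are correlated, and some unlisted ones may predict delirium. The rate does not matter for the seven variables already in the model, and age group and sex are also stratified. The simulation used one outcome per patient, whereas the planned model is a GEE that may use repeated assessments. So the direction is secure but the exact size is not.

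Two further inferences are tempting.
- **Unblinded analysts choosing the covariates.** Section 10.1.6 says "The trial statistician team will be responsible for compiling and curating data into reports for the DSMB" and describes closed DSMB sessions as unblinded, while section 6.3 says "research teams, patients, clinicians, and analysts will remain blinded to the study drug intervention". Compiling reports does not show that the analysts hold the treatment key or see unmasked tables, so the documents do not support this.
- **Habitual caffeine categories as further evidence.** Section 8.2 has intake "categorized into no daily intake or any daily intake"; section 9.4.3 says "the resulting distribution will be analyzed and used to inform the most appropriate categorization of habitual caffeine users". The two need reconciling, but this concerns an interaction for Quality of Recovery and headache severity, not the primary model. It is a separate, minor point.

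Finally, closing the list of examples and defining a three-arm standardised difference could be left to a statistical analysis plan. Neither is counted as a fault here. The >0.20 rule is, because the protocol states it.

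**Conclusion.** The point holds as a cheap improvement, not a threat to validity. The protocol lets chance imbalance decide which covariates join the primary and secondary models. At about 83 per arm the trigger fires by chance for 13%, 33% or 40% of balanced covariates, depending on a choice the protocol does not state. Under the any-pair reading with an assumed 10–20 independent candidates, 4–8 extra terms join 9 parameters on roughly 46 delirious patients. The precision loss is modest (SD of the log odds ratio up roughly 4–13%), the shift away from the null is small, and there is no type I error inflation and negligible power loss. The main harm is that the reported odds ratio depends on what was tabulated and what crossed the line.

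**What to change.** In section 9.4.2, delete the >0.20 rule and state the seven named covariates as the fixed set; they include the stratification factors, age and sex. Remove imbalance adjustment from the secondary models in section 9.4.3 and align the sentence in section 6.3. Keep standardised differences in section 9.4.5 as description only. Add one imbalance-adjusted model, labelled as a sensitivity analysis, and state there how the three arms are compared. Separately, reconcile the habitual-caffeine categories in sections 8.2 and 9.4.3.

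The cost is wording only: no change to sample size, data collection or conduct. The downside is that a large chance imbalance in an unlisted variable would be addressed only in the sensitivity analysis.

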7.3 LOST TO FOLLOW-UP

There is a close proximity in time between study intervention (i.e., study drug infusion) and early postoperative assessments. This assessment will occur when the patient is still hospitalized early in the postoperative course. Thus, loss to follow-up is not anticipated to be a major concern for the primary outcome in this study. However, such loss may occur in certain scenarios, such as unplanned intensive care unit admission with patients remaining intubated postoperatively. Loss to follow-up will thus be reported in study flow diagrams and is accounted for in power calculations (see **Section 9, Statistical Considerations**).

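### Section 9.4.2 makes Little's MCAR test the gate for imputing delirium data, so imputation tends to be withheld under MAR, where it is valid and useful

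*Protocol*

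**What the plan says.** Section 9.4.2 sets the primary model: "The primary analytical test will be a multivariable logistic regression model that will follow the GEE approach". It then fixes a rule for missing outcomes in three parts.

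- The test: "missing delirium data will be assessed for randomness using the Little's Missing Completely at Random Test".
- First branch: "If data are missing at random, imputation will be performed". On how the imputed analysis is to be reported, the same sentence says that "these results will be compared to results with the actual data in the supplementary appendix".
- Second branch: "If data are not missing at random, no imputation will be performed". The only step named instead is that "the Cochran-Armitage test will be used to assess for the proportion of missing data across each arm".

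No other criterion for missing at random is given, so Little's test decides the branch.

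Other sections bear on this:

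- Section 9.4.3 says of the GEE models: "This approach also allows for flexibility with missing data". It specifies empirical estimates with an exchangeable correlation matrix and mentions no weighting.
- Section 7.3 does not expect much loss of the primary outcome, but gives as an example "unplanned intensive care unit admission with patients remaining intubated postoperatively".
- Section 9.2 allows for about 10% dropout.
- Sections 3 and 9.1 supplement the in-person CAM with a chart review method.

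**The concern.** The rule runs together two different conditions. MCAR means that missingness is unrelated to any data, seen or unseen. MAR means that it may depend on observed data but, given those, not on the unseen values. Little's test addresses only the first. Rejecting it is compatible with MAR and with MNAR, and no test on the observed data can tell those two apart. Section 9.4.2 nevertheless reads rejection as not missing at random.

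Imputation is thus offered mainly where the observed data are already representative. It is refused where observed CAM results or patient condition predict missingness and could be used to correct for it. In the second branch the plan compares missing proportions by arm, which corrects nothing, and gives no MNAR analysis, although that is where one is most wanted.

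At stake is whether the handling of the primary endpoint can be trusted when outcomes are lost for reasons related to condition, which is the kind of loss that section 7.3 describes.

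**Working it through.** **Step 1. The rule against what the test can show.**

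| True mechanism | Usual result of Little's test | Action under 9.4.2 | Appropriate? |
|---|---|---|---|
| MCAR | not rejected | impute | harmless, least needed |
| MAR | rejected, if the dependence is strong enough to detect | do not impute | no: MAR imputation is valid here |
| MNAR | often not rejected | impute | MAR imputation alone stays biased |

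**Step 2. How often each branch is taken.** The protocol gives no figure to reproduce, so this is a simulation. From the protocol: 250 patients at 1:1:1, or about 83 per arm; about 10% dropout (9.2); two-sided 0.05 (9.4.1, assumed to apply to Little's test). Everything else is assumed:

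- Each patient has an early result (always observed) and a later result (possibly missing), with logit P(delirium) = −1.2 − 0.5x + b + arm effect. Here x is a standard normal baseline covariate, b a patient effect with SD 1.5, and the arm effects are 0, −0.7 and −1.2.
- Missingness of the later result: constant (MCAR); logit = c + 1.5·early − 0.6x (MAR); logit = c + 2.0·later (MNAR). The constant c is set to give the stated share missing.
- Little's statistic is the sum over missingness patterns of n(m − μ)′Σ⁻¹(m − μ), where m is the pattern mean and μ and Σ are the maximum-likelihood values for the variables observed in that pattern. Degrees of freedom are 3 + 2 − 3 = 2.
- Imputation fills in the prediction from a logistic model on x, early result and arm. There were 1,500 trials per row.

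| Missing | Mechanism | Little rejects (no imputation) | True later rate | Observed only | Imputed |
|---|---|---|---|---|---|
| 5% | MCAR | 4.9% | 22.1% | 22.1% | 22.1% |
| 5% | MAR | 88.3% | 22.2% | 21.5% | 22.2% |
| 5% | MNAR | 19.1% | 22.1% | 19.9% | 20.1% |
| 10% | MCAR | 5.5% | 22.2% | 22.2% | 22.2% |
| 10% | MAR | 98.4% | 22.2% | 20.9% | 22.2% |
| 10% | MNAR | 26.9% | 22.2% | 17.8% | 18.2% |
| 20% | MCAR | 5.1% | 22.2% | 22.1% | 22.2% |
| 20% | MAR | 100.0% | 22.1% | 19.7% | 22.1% |
| 20% | MNAR | 39.5% | 22.1% | 14.0% | 14.7% |

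Under MAR at 10% missing, the observed-only rate is low by 22.2 − 20.9 = 1.3 points, and imputation removes the gap. Under MNAR the rule would impute in 100 − 26.9 = 73.1% of trials, yet MAR imputation recovers only 18.2 − 17.8 = 0.4 of the 22.2 − 17.8 = 4.4 points. These rates pool the arms, so they show which way the gate points, not bias in the treatment contrast.

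**Step 3. Scale for the treatment contrast.** With 250 × 0.9 / 3 = 75 evaluable per arm and incidences of 30% and 15%, the standard error of the log odds ratio is √(1/22.5 + 1/52.5 + 1/11.25 + 1/63.75) = √0.168 = 0.41.

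Seven-visit histories were simulated with dropout of 2% after a negative CAM and 20% after a positive one, and fitted by exchangeable GEE on available data:

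- One set of histories (within-patient correlation not specified, so for scale only) moved the log odds ratio from −0.75 to −0.81, away from the null.
- Histories with patient-effect SDs of 1, 2 and 3 moved it from −0.87 to −0.86, −1.01 to −0.96 and −1.07 to −1.02, toward the null. Any-delirium incidence moved by at most 0.03 on the same scale.

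The largest of these shifts, 0.06, is 0.06 / 0.41 = 0.15 standard errors. In the second set about 14% to 21% of patients dropped out, more than the planned 10%.

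**Step 4. Outer bound.** Ten per cent of 83 is about 8 patients, and 8 / 83 = 9.6 points. That is the full range of one arm's incidence if every missing patient had the event or none did. The planning effects are 30 − 15 = 15 to 30 − 10 = 20 points. This is a worst case, not an expected shift.

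**The case against.** The case for limiting this point is substantial, and most of it stands.

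- **Which analysis is primary.** A reader might infer that the pre-test decides the primary intention-to-treat estimate. The documents do not establish that. Section 9.4.2 sets the imputed results beside those from the actual data in the supplementary appendix, which can be read as keeping observed data primary in both branches. The text is ambiguous; that ambiguity is part of the point.
- **Validity of GEE.** It is tempting to say that unweighted GEE is valid only under MCAR. It is also valid, for the conditional effect, when missingness depends only on covariates in a correctly specified model. Section 9.4.2 lists several, including age, sex, ASA status and baseline cognition. These are all baseline variables, however. Remaining intubated happens after randomisation and is not in the model.
- **Direction of bias.** A reader might infer that the plan overstates the caffeine effect. Step 3 shows that the sign changes with the assumed within-patient correlation.
- **Mitigation.** Chart review, in-hospital assessment and planned admission of at least 72 hours (section 5.1) should all reduce missing outcomes. The intubated patient may be a temporary gap and may be MNAR, where MAR imputation is not enough either.
- **Cochran-Armitage.** With ordered dose arms a trend test is a reasonable description. It can miss a non-monotone difference, but that is secondary.
- **What belongs in the SAP.** The list of imputation variables and the form of the sensitivity analysis can be left to the SAP, which is not shown. The gate cannot, because the protocol itself states it.

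None of this rescues Little's test as the criterion.

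**Conclusion.** The point holds in this form: section 9.4.2 uses a test of MCAR to decide a question about MAR. Its rule tends to impute when imputation is least needed and to withhold it under MAR that depends on observed outcomes or on variables outside the model. This follows from the null hypothesis of the test and needs no simulation. The simulated frequencies (about 5% rejection under MCAR; 88% to 100% under MAR) only illustrate it, and rest on assumed event rates and fairly strong dependence.

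The effect on the trial's result is uncertain in size and direction, and probably modest with chart review and about 10% dropout. The documents do not show that the primary estimate is materially biased or that its bias favours caffeine. Severity: should be fixed.

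**What to change.** In section 9.4.2:

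1. Delete Little's test as the condition for imputing.
2. State which analysis is primary: observed-data or imputed.
3. Perform multiple imputation, or weighted GEE, under MAR regardless of any test. Use arm, baseline covariates, observed CAM, CAM-S and RASS results, and chart-review data. The variable list may sit in the SAP.
4. Add a delta-adjusted or tipping-point sensitivity analysis for MNAR.
5. Report missing delirium outcomes by arm and reason, so that patients still intubated are visible.

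In section 9.4.3, qualify the sentence on GEE and missing data: unweighted GEE is valid under MCAR, or when missingness depends only on covariates in the model.

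The cost is protocol and SAP wording plus modest programming. Sample size and data collection do not change. The change should be made before unblinding.
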